9.3.3.2 Safety endpoints

- DLTs

The incidence of DLTs (in DLT-evaluable patients, see section 4.1.3) by dose level will be summarized with counts and percentages.

- TEAEs

A TEAE is defined as an AE that started or worsened at or after the start of study treatment.

TEAEs will be summarized with counts and percentages. These will be provided for the incidence of, but not limited to: any TEAE, any serious TEAE, any grade 3-5 TEAE, any drug-related TEAE, any serious and drug-related TEAE, any grade 3-5 and drug-related TEAE, temporarily discontinued due to a TEAE, permanently discontinued due to a TEAE, death. TEAE incidence frequencies by system organ class and preferred term will also be provided.

- Safety laboratory findings and vital signs

Safety laboratory findings and vital signs measurements will be summarized accordingly (if categorical or continuous data). Laboratory results will be summarized using SI units as appropriate.

Further details on analyses to be performed will be specified in the final statistical analysis plan (SAP).

9.3.4 Exploratory endpoint analysis

- PFS on next-line anti-cancer treatment (PFS2)

PFS2 is defined as the time from the first day of study treatment until the date of second radiological disease progression (i.e., progression on next-line anti-cancer treatment) or death and will be summarized using Kaplan-Meier estimates.

Patients with missing data (i.e., without second radiological disease progression) will be censored at the last time known to be alive.

- OS

OS is defined as the time from the first day of study treatment until the date of death and will be summarized using Kaplan-Meier estimates. Patients with missing data will be censored at the last time known to be alive.

9.3.5 Other analyses

Other sensitivity, secondary, and exploratory analyses such as PK, immunogenicity, biomarker exploratory analyses, and circulating tumor DNA will be described in the final SAP.

9.4 Interim analysis

An analysis for futility will be performed when the sample size is considered enough for such analysis. Efficacy data and outputs will also be a part of the IDMC review.

Assuming a desired ORR, the futility analysis will be based on a comparison against a minimal ORR considered as both statistically and clinically relevant improvement as compared to the benchmark ORR. An 80% CI using the exact method²⁶ for the ORR (alpha = 0.2, alpha = 0.1 one-sided) will be used.

The analysis will be based on the efficacy population.

If the ORR is:

1. lower than the minimal ORR, and
2. the 80% CI for the ORR does not include the minimal ORR,

it will be concluded that the combination treatment is futile as compared to cetuximab treatment alone and thus the study will be discontinued. However, patients still on treatment can continue combination therapy if recommended by the IDMC.

The criteria for conclusion of futility are defined as follows:

- Benchmark ORR = 20%²¹; minimal ORR = 28.8%; desired ORR = 36.8%
- N = 16 patients if the number of responses is less than 2 (r < 2)

Additionally, the ORR will be evaluated on an ongoing basis (without stopping of recruitment). Other efficacy endpoints will be used as supportive information.

9.5 Sample size determination

In the safety cohorts, the traditional 3+3 design dose escalation will be applied. Therefore, 3 to 6 DLT-evaluable patients per dose level will be included in a cohort. The estimated number of patients is 6-12.

The overall sample determined in this trial is 52 patients in efficacy population (see section 9.2.3) which includes patients from the safety cohorts and the main cohort.

The total sample size is based on a Bayesian calculation: Markov chain Monte Carlo has been used for the sample size determination. Assuming a desired ORR for the number of responses, and a uniform prior distribution between 0 and 1, the sample size of 52 patients will ensure at least 80% posterior probability to achieve an effect above the minimal ORR:

- Benchmark ORR: 20%²¹
- Minimal ORR (relative increase, absolute increase): 28.8% (1.44, 8.8%)
- Desired ORR (relative increase, absolute increase): 36.8% (1.84, 16.8%)

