4.1.1 Study design

First, 3 patients will be recruited sequentially so that the first administrations of nanrilkefusp alfa to the first and second patients will be 7 days apart and the second and third patients will not be dosed on the same day. These patients will be treated with cetuximab in combination with 9 µg/kg nanrilkefusp alfa, a dose one dose level below the RP2D as determined in study SC103 (AURELIO-03) which evaluated nanrilkefusp alfa at doses up to 12 µg/kg in combination with pembrolizumab. Please see section [6.1](#) for more details on administration of study interventions.

After the last patient in the 9 µg/kg safety cohort completes the first treatment cycle of 21 days, i.e., the DLT assessment period, an internal safety committee (ISC) will review the safety data.

If at least one patient in the initial 9 µg/kg safety cohort experiences a DLT, an additional 3 patients will be recruited into the 9 µg/kg safety cohort. The ISC will review the safety data of these 3 additional patients and decide whether it is safe to increase the dose to 12 µg/kg nanrilkefusp alfa in combination with cetuximab in the second safety cohort or whether the study should proceed with 9 µg/kg nanrilkefusp alfa or with 6 µg/kg nanrilkefusp alfa.

If there are no safety concerns in the initial 9 µg/kg safety cohort, the study will proceed to the second safety cohort and sequentially recruit another 3 patients who will receive 12 µg/kg nanrilkefusp alfa in combination with cetuximab. As in the 9 µg/kg cohort, the first administrations of nanrilkefusp alfa to the first and second patients will be 7 days apart and the second and third patients will not be dosed on the same day. Safety in the 12 µg/kg cohort will be evaluated by the ISC after the last patient completes the DLT assessment period (first treatment cycle of 21 days).

If at least one patient in the 12 µg/kg safety cohort experiences a DLT, an additional 3 patients will be recruited into the 12 µg/kg safety cohort. The ISC will review the safety data of these 3 additional patients and decide whether it is safe to proceed to the main cohort with patients receiving 12 µg/kg nanrilkefusp alfa in combination with cetuximab or whether the study should continue at a lower nanrilkefusp alfa dose.

If there are no safety concerns in the 12 µg/kg safety cohort, the study will proceed to the main cohort and recruit patients who will receive 12 µg/kg nanrilkefusp alfa in combination with cetuximab.

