Patients in the initial 9 µg/kg safety cohort may also have a dose increase to 12 µg/kg nanrilkefusp alfa in the next treatment cycle at the discretion of the investigator if there are no safety concerns in the 12 µg/kg safety cohort.

Patients in the safety cohorts who do not fulfill the DLT evaluability criteria (see section [4.1.3](#)) for any reason other than DLT during the DLT assessment period will be replaced until at least 3 patients per cohort have completed their DLT assessment period.

In the main cohort of the study, patients will be treated with nanrilefusp alfa in combination with cetuximab in 21-day cycles. An independent data monitoring committee (IDMC) will be established to review safety and efficacy data at certain time intervals, or when the interim analysis for futility is triggered, once the main cohort of the study starts.

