4.1.3 DLT evaluability

DLT evaluability is defined as follows:

- Patient completed the first 21-day cycle (DLT assessment period of 21 days)
- Patient received all administrations of nanrilkefusp alfa during the DLT period as per schedule (± 1 day)
- Patient received cetuximab as per schedule (± 1 day)

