4.3 Justification for dose

4.3.1 Nanrilefusp alfa (SOT101)

In study SC103 (AURELIO-03), 12 µg/kg of nanrilefusp alfa was determined to be the RP2D for both nanrilefusp alfa monotherapy and nanrilefusp alfa combined with pembrolizumab. To ensure that it is safe to administer nanrilefusp alfa at this RP2D together with cetuximab, an initial safety cohort of 3 patients will be treated with cetuximab in combination with 9 µg/kg nanrilefusp alfa, a dose one dose level below the RP2D determined in study SC103 (AURELIO-03). These 3 patients will be closely observed, and safety data collected during the DLT assessment period, i.e., first 21-day treatment cycle, will be evaluated by the ISC. If the safety of nanrilefusp alfa at 9 µg/kg in combination with cetuximab is acceptable, another safety cohort of 3 patients will be treated with cetuximab in combination with 12 µg/kg nanrilefusp alfa, the RP2D determined in study SC103 (AURELIO-03). Safety in the 12 µg/kg cohort will be evaluated by the ISC after the last patient completes the DLT assessment period. If there are no safety concerns in the 12 µg/kg safety cohort, the study will proceed to the main cohort and recruit patients who will receive 12 µg/kg nanrilefusp alfa in combination with cetuximab. If there are safety concerns at the 9 µg/kg and/or 12 µg/kg nanrilefusp alfa safety cohorts, the ISC will decide how to proceed as described in section 4.1.1.

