10 SUPPORTING DOCUMENTATION AND OPERATIONAL CONSIDERATIONS

10.1 Appendix 1: Regulatory, ethical, and study oversight considerations

10.1.1 Regulatory and ethical considerations

The Protocol, ICF, and appropriate related documents must be reviewed and approved by an IRB/IEC (in the US)/EC (in the EU) constituted and functioning in accordance with ICH Guideline E6 Good Clinical Practice (GCP)²⁷ and any local regulations, and by the competent authority (CA). Any Protocol amendment or revision to the ICF will be resubmitted to the IRB/IEC (in the US)/EC (in the EU) and to the CA for review and approval, except for changes involving only logistical or administrative aspects of the study (e.g., change of clinical research associates [CRAs], change of telephone numbers). Documentation of IRB/IEC (in the US)/EC (in the EU) compliance with ICH E6 and any local regulations regarding constitution and review conduct will be provided to the sponsor.

A signed letter of study approval from the IRB/IEC (in the US)/EC (in the EU) chairman must be sent to the principal investigator or, if regionally required, the head of the medical institution with a copy to the sponsor before study start and the release of study interventions to the site by the sponsor or its designee. If the IRB/IEC (in the US)/EC (in the EU) decides to suspend or terminate the study, the investigator (or if regionally required, the head of the medical institution) will immediately send the notice of study suspension or termination by the IRB/IEC (in the US)/EC (in the EU) to the sponsor.

Study progress is to be reported to IRBs/IECs (in the US)/ECs (in the EU) and to CAs annually (or as required) by the investigator or sponsor, depending on local regulatory obligations. If the investigator is required to report to the IRB/IEC (in the US)/EC (in the EU), s/he will forward a copy to the sponsor at the time of each periodic report.

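### The expansion trigger in protocol 4.1.1 and SAP 2.1 (one or more DLTs in the first 3) does not match the traditional 3+3 named in protocol 9.5 and SAP 2.3 when 2/3 or 3/3 patients have a DLT

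*Protocol*

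**What the plan says.** Protocol 9.5 states that in the safety cohorts "the traditional 3+3 design dose escalation will be applied", and draws from this 3 to 6 DLT-evaluable patients per dose level and 6 to 12 patients in all. SAP 2.3 says the same. Neither section writes out the 3+3 decision rule.

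The action rule is in protocol 4.1.1 and is repeated in SAP 2.1. The condition is that one or more patients in the first cohort of 3 "experiences a DLT, an additional 3 patients will be recruited into the" same cohort. This applies at 9 µg/kg and again at 12 µg/kg. There is no separate branch for 2/3 or 3/3. After the additional 3 patients the ISC reviews their data and chooses among going up, staying or going down, with no DLT count attached.

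The ISC also has a look before any expansion. Once the last patient at 9 µg/kg finishes cycle 1, "i.e., the DLT assessment period, an internal safety committee (ISC) will review the safety data", and 4.1.1 sets a matching review at 12 µg/kg. Protocol 10.1.11 lets the ISC continue, modify or stop recruitment and leaves its procedures to the ISC Charter. Protocol 4.3.1 adds that, where there are safety concerns, "the ISC will decide how to proceed as described in section 4.1.1".

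**The concern.** The two descriptions agree at 0/3 and at 1/3. They part at 2/3 and 3/3. A traditional 3+3, as the term is ordinarily understood, treats that dose as too toxic and enrols no one else at it. The rule in 4.1.1, followed literally, treats 3 more patients at it.

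At stake is the safety of up to 3 patients at a dose that the named design would already have closed. Sites, ethics committees and the ISC also cannot tell from the text which rule governs. The pointer in 4.3.1 does not settle it, because it leads back to 4.1.1, where the broad trigger sits.

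**Working it through.** **1. The plan's own figure.** Two dose levels (9 and 12 µg/kg) with 3 to 6 DLT-evaluable patients each give 2 × 3 = 6 to 2 × 6 = 12. This reproduces the stated 6 to 12. It fits either reading of the expansion rule, so it does not show which one was meant.

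**2. The rules side by side, first 3 patients at a dose.**

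| DLTs in first 3 | Traditional 3+3 (standard meaning) | Protocol 4.1.1 / SAP 2.1 as written |
|---|---|---|
| 0 | go on | go on, if no safety concerns |
| 1 | add 3 at same dose | add 3 at same dose |
| 2 or 3 | no more at this dose | add 3 at same dose |

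**3. How often the last row arises.** Let X be the number of DLTs in the first 3 patients, X ~ Binomial(3, p). The documents give no DLT rate for the combination, so p = 0.1, 0.2 and 0.3 are assumptions.

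P(X ≥ 2) = 3p²(1 − p) + p³

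- p = 0.1: 3 × 0.01 × 0.9 + 0.001 = 0.028
- p = 0.2: 3 × 0.04 × 0.8 + 0.008 = 0.104
- p = 0.3: 3 × 0.09 × 0.7 + 0.027 = 0.216

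**4. Size.** Each such cohort adds 3 patients if nobody intervenes, so the expected extra exposures per cohort are at most 3 × P(X ≥ 2). The share of written-rule expansions that the named design would not allow is P(X ≥ 2) / P(X ≥ 1), with P(X ≥ 1) = 1 − (1 − p)³.

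| Assumed p | P(X ≥ 1) | P(X ≥ 2) | Share of expansions affected | Upper bound, extra exposures per cohort |
|---|---|---|---|---|
| 0.1 | 0.271 | 0.028 | 10.3% | 0.08 |
| 0.2 | 0.488 | 0.104 | 21.3% | 0.31 |
| 0.3 | 0.657 | 0.216 | 32.9% | 0.65 |

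The last column assumes that the ISC reviews 2/3 or 3/3 DLTs and lets expansion proceed. Any ISC action lowers it. Protocol 4.3.1 records 12 µg/kg as the recommended phase 2 dose both alone and with pembrolizumab, so the documents give no reason to favour the upper end of the range.

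**The case against.** The strongest reply is that protocol 9.5 contains no stopping count. It names a design and takes a patient range from it, and the only written action rule is 4.1.1. That is correct. A reader might infer that 9.5 itself orders the dose to stop, so that two written instructions collide; the text does not say so. The mismatch is between a written trigger and the standard meaning of the label. It remains a mismatch, because nothing in either document says that the label is meant in some other sense.

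A second reply is that expansion is supervised. The ISC sees the first 3 patients at each dose after cycle 1 and may stop recruitment. The first two patients start 7 days apart, and the second and third are not dosed on the same day. After expansion, 4.1.1 allows a lower dose. All of this stands, and it rules out reading the plan as automatic or unreviewed expansion. It limits the consequence without correcting the trigger. The Charter may contain counts, but it cannot repair the protocol: a Charter that stops at 2/3 departs from 4.1.1, and one that follows 4.1.1 departs from the named design.

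Two wider readings should be set aside.

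- A reader might count as a further conflict the cohorts with 1/3 and then at least one more DLT in the next 3. Section 4.1.1 is silent on a count there, and the named 3+3 can fill that silence, so it is a gap in wording and not a contradiction.
- A reader might infer from protocol 4.1.3, which requires that "Patient received all administrations of nanrilkefusp alfa during the DLT period as per schedule", that a patient whose dosing stopped for a DLT drops out of the count. Section 4.1.1 largely prevents this, since only patients not evaluable "for any reason other than DLT during the DLT assessment period will be replaced", and SAP 5.6.2 counts patients with a DLT whatever number of doses they received.

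**Conclusion.** The point holds as an inconsistency at 2/3 and 3/3 DLTs, at both dose levels and in both documents. Followed literally, 4.1.1 treats 3 more patients at a dose that the named design would close. At assumed true DLT rates of 10%, 20% and 30% this concerns 2.8%, 10.4% and 21.6% of cohorts, with at most 0.08, 0.31 and 0.65 extra exposures per cohort.

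The conclusion rests on the standard meaning of a traditional 3+3. The size rests on the assumed rates and on no ISC intervention. The wording mismatch is certain; whether any patient would be affected depends on ISC conduct and on a Charter that was not available. The 3 to 6 per dose, the 6 to 12, the total of 52 and the response-rate analysis are not affected. It is worth correcting because it concerns a safety rule and the correction adds no patients.

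**What to change.** In protocol 4.1.1 and SAP 2.1:

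- Change the expansion condition from one or more patients to exactly one of the first 3 patients, at both doses.
- State that 2 or more DLTs in the first 3, or in the pooled 6, close that dose and lead to de-escalation (12 to 9 µg/kg, or 9 to 6 µg/kg).
- State that escalation, or opening the main cohort at a dose, needs 0/3 or at most 1/6.
- Leave the ISC free to be more cautious, and align its Charter.

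As a minor cross-reference, bring protocol 4.1.3 into line with SAP 5.6.2 so that a patient with a DLT counts as evaluable.

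The cost is a protocol amendment. Protocol 10.1.1 says that "Any Protocol amendment or revision to the ICF will be resubmitted to the IRB/IEC" or ethics committee and to the competent authority, with an exception only for logistical or administrative changes, which this is not. SAP 2.1 and the Charter need matching edits. The ISC loses the latitude to expand or continue a dose after 2 or more DLTs. No extra patients are needed, since at most 6 at each of two dose levels stays within 6 to 12.

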9.3.2 Primary endpoint analysis

The ORR is defined as the proportion of patients with complete response according to RECIST 1.1 (CR) or partial response according to RECIST 1.1 (PR). ORR will be analyzed and presented as a point estimate and a 95% CI. Patients with missing data will be considered as non-responders.

Sensitivity analyses will include the use of:

- ASaT and PP populations
- No imputation of missing data

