2.3. Sample Size and Power

In the safety cohorts the traditional 3+3 design dose escalation will be applied. Therefore, 3 to 6 DLT-evaluable patients per dose level will be included in a cohort. The estimated number of patients is 6-12. The overall sample determined in this trial is 52 patients in efficacy population which includes patients from the safety cohorts and the main cohort.

The total sample size is based on a Bayesian calculation: Markov chain Monte Carlo has been used for the sample size determination. Assuming a desired Objective Response Rate (ORR) for the number of responses, and a uniform prior distribution between 0 and 1, the sample size of 52 patients will ensure at least 80% posterior probability to achieve an effect above the minimal ORR:

- Benchmark ORR: 20%¹
- Minimal ORR (relative increase, absolute increase): 28.8% (1.44, 8.8%)
- Desired ORR (relative increase, absolute increase): 36.8% (1.84, 16.8%)

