5.5.1. Primary Efficacy Analysis

The ORR is defined as the proportion of patients with Complete Response according to RECIST 1.1 (CR) or Partial Response according to RECIST 1.1 (PR). ORR will be analyzed in the efficacy population and presented as a point estimate along with 95% Clopper-Pearson CI. Patients with missing data will be considered as non-responders.

To determine the ORR, the BOR (see [Section 5.5.3.1](#)) of each patient will be computed according to RECIST v1.1 criteria.

ORR according to RECIST 1.1 will also be listed for enrolled population.

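### Is it wrong to say that 52 patients give at least 80% posterior probability of exceeding the minimal ORR?

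*Protocol*

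**What the plan says.** Protocol 9.5 plans the trial size as follows: "The overall sample determined in this trial is 52 patients in efficacy population". It describes a Bayesian calculation by Markov chain Monte Carlo. The governing condition is "Assuming a desired ORR for the number of responses, and a uniform prior distribution between 0 and 1", and under it "the sample size of 52 patients will ensure at least 80% posterior probability to achieve an effect above the minimal ORR". The benchmark is 20%, the minimal ORR 28.8% and the desired ORR 36.8%. SAP 2.3 repeats the statement.

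The primary analysis is separate. Protocol 9.3.2 says "ORR will be analyzed and presented as a point estimate and a 95% CI". SAP 5.5.1 has the ORR "presented as a point estimate along with 95% Clopper-Pearson CI". Protocol 9.1 plans no formal hypothesis test, and Protocol 9.3.1 and SAP 5.1 call the analyses descriptive. The only decision rule tied to the 28.8% is the interim futility rule (Protocol 9.4, SAP 5.6.12). It uses an exact 80% interval and a limit of fewer than 2 responses in 16 patients.

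**The concern.** A posterior probability depends on the responses observed, so no sample size can ensure it in advance. Taken without its condition, the sentence reads as a promise that the trial will reach 80%. The natural check is how often it would do so if the treatment performs as hoped, and the answer is about two trials in three. The sizing quantity also appears nowhere in the planned output. And if the result is exactly the one hoped for, the 95% interval still contains 28.8%. If all this were a defect, the only stated rationale for 52 patients would credit the design with a property it lacks, and the final report could not show whether the sizing goal was met.

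**Working it through.** **Inputs** (Protocol 9.5, SAP 2.3): n = 52; uniform prior, i.e. Beta(1,1); minimal ORR 28.8% = 20% × 1.44; desired ORR 36.8% = 20% × 1.84; target of at least 80%.

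**The plan's own figure.** After r responses in 52 the posterior is Beta(r + 1, 53 − r). The conjugate form is exact, so simulation is not needed to check it. The number of responses at the desired ORR is 0.368 × 52 = 19.1, i.e. 19.

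| Responses in 52 | P(ORR > 28.8%) |
|---|---|
| 17 | 0.755 |
| 18 | 0.837 |
| 19 | 0.899 |
| 20 | 0.941 |

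- Responses set at the desired ORR (19 of 52): 0.899.
- Posterior averaged over r ~ Binomial(52, 0.368): 0.819.

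Both are at least 0.80. The stated figure reproduces on each of the two natural readings of the condition.

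**The 68%.** The smallest r with a posterior of at least 0.80 is 18. The chance of 18 or more responses in 52 is:

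| True ORR | P(X ≥ 18) |
|---|---|
| 36.8% | 67.7% |
| 28.8% | 21.7% |
| 20% | 1.0% |

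The futility look at 16 patients changes the first figure only to 67.6%. These numbers are right. They give the long-run frequency of reaching the level at a fixed true ORR, whereas the plan states the level of the posterior given responses at the desired ORR. The first can be 68% while the second is 90%, and there is no contradiction.

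**Does the criterion have to yield 52?** If the count is allowed to be fractional, r = 0.368n, the posterior passes 0.80 at about n = 18. That means 0.368 × 18 = 6.6 responses, which cannot be observed. With the count rounded down to whole patients, the posterior is still below 0.80 at n = 32, 35 and 38, and it stays at or above 0.80 under every rounding only from n = 39. The averaged version passes 0.80 at n = 44. So 52 meets the criterion with some margin. The documents say at least 80%; they do not call 52 the smallest size that qualifies.

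**The planned interval.** At 19 of 52 the Clopper-Pearson 95% interval is 23.6% to 51.0%. It contains 28.8%, but it lies wholly above the 20% benchmark for cetuximab alone. A lower limit above 28.8% needs 23 of 52 (at 22 of 52 it is 28.73%), which has a 16.6% chance at a true ORR of 36.8%. Neither document asks the final 95% interval to exclude 28.8%, so that percentage describes a success rule the trial does not have.

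**The case for a change.** The strongest reply is that the condition empties the statement. It assumes the hoped-for result and then reports that the posterior is favourable, while the verb still tells the reader that something is assured. Protocol 4.2 says the study is meant to support a decision on a confirmatory trial, and whoever takes that decision would want to know how often the design reaches its own benchmark. No reading tested gives 52 as the minimum, and the sizing quantity is not reported at the end.

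Part of this stands. The verb is loose, the 68%, 22% and 1% are not stated, and the sizing criterion is not linked to the planned output. None of it makes the stated figure wrong. The condition comes before the claim in the same sentence and fixes its meaning. Sizing on one criterion and reporting an exact interval is not inconsistent in a descriptive single-arm study whose primary objective is estimation. Anyone who wants the posterior can compute it from r and n under the stated prior, because both will be reported.

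**Conclusion.** The concern does not hold. With its condition included, the sentence is correct: the posterior probability is 0.899 at 19 of 52 responses and 0.819 on average at a true ORR of 36.8%, against a stated level of 80%. The 67.7% answers a question the documents do not raise. Following the plan as written gives a sound ORR with an exact 95% interval, and no result or decision depends on the missing operating characteristics. Stating them would be a reporting preference.

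This rests on the uniform prior as stated, on all 52 patients counting in the efficacy population, and on reading the opening clause of the sentence as setting the response count, either at its expected value or as a binomial draw at 36.8%.
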